1.0 Background

1.0 Introduction

The intent of this protocol is to reduce the burden of pleural effusion in patients with metastatic breast cancer such that the time of indwelling catheter can be reduced. The hypothesis is that pleural effusion tumor burden is dictated by the amplification and expansion of progenitor cells that could be inhibited by pushing the stem/progenitor equilibrium back towards a more quiescent cancer stem cell using the histone deacetylase (HDAC) inhibitor, valproic acid (VPA). Patients who could benefit from an indwelling catheter based on MDACC algorithms for placement will be randomized to 10 weeks of valproic acid or placebo and a pleural catheter placed. Time to catheter removal based on MDACC algorithms will be the primary endpoint. Serial fluid samples will be examined to validate the translational hypothesis and ensure HDAC inhibition occurs.

[figure not shown]

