The second issue to be discussed from the two trials is that, although limited, **preclinical evidence does suggest that like most "targeted therapies", the chronic administration of VPA is required to achieve the best results(42, 43)**. This may have implications regarding the maximum tolerated dose, being possible that short-term administrations of VPA (three or five days) could allow to administer higher doses but for chronic administrations doses such as those encountered safe in the first study would be more suitable, particularly in combination therapies with other cytotoxic or cytostatic drugs. **In summary, it seems that doses between 20 and 60 mg/kg of VPA can be appropriate for further testing in solid tumors as H3 and H4 hyperacetylation in tumors is achievable in most patients.**

Phase I-II studies

A third study with VPA combined with epirubicin was recently published. This was a phase I-II study in patients with advanced solid tumor malignancies, an ECOG performance status of 0-2, and adequate organ function. Prior anthracyclines were permitted (doxorubicin ≤ 300 mg/m² and epirubicin ≤ 600 mg/m²). In this study an intravenous loading dose of VPA was followed by five oral doses administered every 12 h beginning 1 h after the loading dose, though later in the study, the intravenous loading dose was replaced with an oral loading dose. Dose escalation started on 15 mg/kg up to 160 mg/kg. On day 3, 4 h after the last dose of VPA, epirubicin was administered by intravenous infusion in cycles of 21 days. The trial allowed for maximal cumulative doses of 750 mg/m² for epirubicin (or epirubicin equivalent) or the use of a cardioprotectant in patients with clearly documented benefits beyond this dose.

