1.3 Rationale

On the basis of the results from the studies cited above, we hypothesize that VPA may decrease pleural effusion production in cancer patients by inducing quiescence in the tumor cells through a dedifferentiation mechanism. To test this hypothesis, we propose to treat breast cancer patients who need an indwelling pleural catheter due to malignant pleural effusion with 10 weeks of VPA and compare to those treated with placebo. This compound inhibits histone deacetylase, and has shown a relatively safe profile at a dose of 30 mg/kg/day divided into three doses even in combination with second and third line chemotherapy drugs. This dose is expected to lead to hyperacetylation of H3 and H4 in most patients. Successful results of this study may improve the symptom

burden of end stage cancer patients with recurrent pleural effusion, and may reduce the expenses associated with their disease.

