2.0 Objectives

2.0 Study Objectives

2.1 Research Design and Methods

Our goal is to better understand the biology of breast cancer stem cells and pleural effusion formation to improve therapy of malignant pleural effusion in breast cancer patients. Based on our preclinical studies described in the background section, a clinical trial is planned to answer specific questions regarding the role of histone deacetylation and effect of its inhibition on breast patients with MPE. In this study, eligible patients with recurrent symptomatic MPE who need an indwelling pleural catheter based on MDACC algorithms for placement will have one placed and will receive 10 weeks of VPA or placebo.

The first aim is to achieve a beneficial clinical effect of VPA on patients with MPE. The specific question is if VPA alters pleural effusion re-accumulation following placement of an indwelling pleural catheter to the extent that it will enable significant shortening of time to removal of the catheter compared to placebo. Additional aims will analyze the biology of histone deacetylation inhibition in MPE and will help to develop biomarkers of activity and noninvasive monitoring to such therapy:

The second aim is to analyze the amount of daily fluid drained with therapy. Patients will be provided a daily fluid drainage diary.

The third aim is to assess radiographic and clinical correlates using standard of care testing and assessment: Chest x-ray and CT to study effect on primary tumor burden and assessment of overall survival.

Our fourth aim is to study biological correlates. We will study the level of H3 and h4 hyperacetylation and inflammatory cytokines in the effusion and in the serum at baseline and at week 2. Fluid will be collected and stored if applicable from visits at baseline, at week 2, 6, and 10. We plan to study expression of stem cell markers on cells from effusion to demonstrate inhibitory effect of VPA on these cells. Urine will be collected and stored if applicable at baseline, weeks 2, 6, and 10 for correlative studies. Finally, we will study the effect of VPA therapy on level of circulating tumor cells.

Our fifth aim is to assess drug effect on patient symptoms, dyspnea and exercise tolerance using the EuroQOL, St George's respiratory questionnare and six-minute walk test respectively.

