3.4 On-Study Evaluations

On the day of indwelling intrapleural catheter placement the patient's pleural fluid will be drained, recorded and sent for cytology review. On the day of indwelling intrapleural catheter placement patients will receive VPA or **placebo** if cytology is positive. Patients will be provided a diary to record drainage from home.

Patients will be treated for the whole period of 10 weeks, and clinical course of disease will be monitored throughout this time. (Note: evaluations may be done within \pm 7 business days of the date specified in the protocol).

Patients will initially receive daily oral VPA 15 mg/kg/day divided in three doses or placebo divided in three doses. Based on the patient's bmi, obese patient dosing will be based on the adjusted body weight calculated using the MD Anderson Clinical

Calculator Formula (<http://inside2.mdanderson.org/apps/calculators/calc1.cfm>). If the patient tolerates the reduced dose for 10 consecutive days then the VPA dose will increase to 30 mg/kg/day divided into three doses or placebo divided into three doses. The patient will be contacted by phone to assess tolerance and instruction to increase dose. Daily dose in mg will be divided by 250 mg and rounded down to a whole number of capsules to determine the number of VPA tablets or placebo tablets to be taken 3 times per day.

Evaluations may occur any time during weeks 2, 6, and 10.

- 3.4.1 Patients will document daily amount of pleural fluid drainage.
- 3.4.2 Patients will be evaluated at weeks 2, 6, and 10 with complete interim histories and physical examinations including measurement of vital signs, performance status, weight and medical history.
- 3.4.3 Patients will complete a EQ-5D and St. George's respiratory questionnaire, at weeks 2, 6, and 10 in person, via telephone or electronic media.
- 3.4.4 Blood samples for CBC with differential, platelet count, and PT/PTT/INR, serum and plasma banking, and optional CTC (if patient agrees) assessment will be collected prior to treatment and at weeks 2, 6 and 10.
- 3.4.5 Tests to measure serum electrolytes, BUN, creatinine, glucose, albumin, alkaline phosphatase, AST or ALT, LDH, total bilirubin, amylase, lipase, magnesium and ionized calcium will be performed at weeks 2, 6, and 10.
- 3.4.6 Optional urine (if patient agrees) will be collected prior to treatment and at weeks 2, 6 and 10.
- 3.4.7 Chest x-ray will be performed immediately after catheter placement and at weeks 2, 6, and 10.

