* If the patient tolerates the reduced dose for 10 consecutive days then the VPA dose will increase. This will be assessed at the 2 week visit. The patient will be contacted by phone to assess tolerance and instruction to increase the dose.

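### Histone acetylation is planned only at baseline and week 2, so target inhibition is not measured at established full dose (30 mg/kg/day)

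*Combined protocol and SAP*

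**What the plan says.** **Assay schedule.** The fourth aim in section 2.1 is to study "the level of H3 and h4 hyperacetylation and inflammatory cytokines in the effusion and in the serum at baseline and at week 2". Later fluid is mentioned separately: "Fluid will be collected and stored if applicable from visits at baseline, at week 2, 6, and 10". No H3/H4 assay is assigned to weeks 6 or 10. Objective 2.3.2 names the assay without a time point, and section 6.0 adds none.

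**Dose schedule.** Sections 3.4 and 5.0 start patients at 15 mg/kg/day, then: "If the patient tolerates the reduced dose for 10 consecutive days then the VPA dose will increase to 30 mg/kg/day". Both sections mention a phone call to assess tolerance and instruct the increase, without dating it. The footnote to the Study Parameters table adds "This will be assessed at the 2 week visit", followed by the same phone contact.

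**Intended dose.** Section 1.3 says of 30 mg/kg/day: "This dose is expected to lead to hyperacetylation of H3 and H4 in most patients". The summary of phase I studies in section 1.2.1 concludes that "doses between 20 and 60 mg/kg of VPA can be appropriate for further testing in solid tumors".

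**Purpose.** Section 1.0 states: "Serial fluid samples will be examined to validate the translational hypothesis and ensure HDAC inhibition occurs".

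**The concern.** The one on-treatment measurement of the drug's molecular target falls at the change from the lead-in dose to the full dose, whereas the rationale ties the expected effect to the full dose. If week 2 shows no rise in acetylation, the trial cannot say whether 30 mg/kg/day fails to inhibit HDAC or whether the sample simply came too early. If the primary result is null, there is no planned evidence on whether the target was inhibited during most of the treatment period.

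Nothing else planned fills the gap. Valproic acid serum levels are drawn only where indicated or for adverse events (section 5.2 and the Study Parameters table), so there is no routine exposure check. The flow cytometry in section 6.0 measures quiescence and stem-cell markers, not HDAC inhibition.

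**Working it through.** The plan gives no figure to reproduce. The check is calendar arithmetic on its own schedule, with drug day 1 as the day of catheter placement.

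**1. Days at full dose when the week-2 sample is drawn**
- Ten tolerated days make day 11 the earliest full-dose day. If a partial day 1 (allowed in section 5.0) is not counted, it is day 12.
- The dose-escalation caption in section 5.2 ties visits to the week on drug, so week 2 is days 8 to 14. Section 3.4 allows any day in that week.
- Visit first, then call: 0 days at full dose.
- Call first, on day 11: draws on days 8 to 10 come before the step-up. Draws on days 11 to 14 come 0 to 3 days after it (14 − 11 = 3; with day 12, 14 − 12 = 2).
- Section 3.4 also has a ±7 business-day note, equal to 9 to 11 calendar days. From day 14 the latest draw is day 23 to 25, at most 25 − 11 = 14 days after a day-11 step-up. The earliest is day 3 to 5, at the starting dose. The window permits a full-dose draw but does not plan one.

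**2. Full-dose days with no planned H3/H4 measurement after week 2**
- Step-up on day 11: 70 − 11 + 1 = 60 of 70 (86%).
- Step-up on day 15: 70 − 15 + 1 = 56 of 70 (80%).
- If the visit slips to day 23 to 25 and the call follows it, step-up falls on day 24 to 26: 70 − 24 + 1 = 47 to 70 − 26 + 1 = 45 of 70 (67% to 64%).

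**3. Dose actually taken, after rounding down to 250 mg capsules** (weights of 50 to 100 kg assumed)
- Lead-in: 11.4 (750/66) to 15.0 mg/kg/day; at 70 kg, 1000/70 = 14.3.
- Full dose: 25.9 (1500/58) to 30.0 mg/kg/day; at 70 kg, 2000/70 = 28.6.

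**4. What a week-6 sample would give** (days 36 to 42)
- Step-up on days 11 to 15: 36 − 15 = 21 to 42 − 11 = 31 days after it.
- Step-up as late as day 26: 36 − 26 = 10 days at the shortest.

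**5. Fluid available at week 6.** Assume exponential times to removal, so the fraction with a catheter still in is 2^(−t/median), with 38 patients per arm.

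| Medians (active / control) | Day 36 | Day 42 |
|---|---|---|
| 28 / 56 days | 38 × (0.410 + 0.640) = 39.9 | 38 × (0.354 + 0.595) ≈ 36 |
| 55 / 110 days | 38 × (0.635 + 0.797) = 54.4 | 38 × (0.589 + 0.767) = 51.5 |

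At the design medians that is about 36 to 40 of 76. Deaths and removals for other reasons lower it further.

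**The case against.** The case for leaving the plan alone has real content.

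- **Week 2 is informative if positive.** A rise over placebo at 15 mg/kg/day would show that the lead-in dose is enough and would support inhibition at the higher dose. This stands; only a negative result is ambiguous.
- **Early sampling is reasonable.** The cervical cancer phase I study found hyperacetylation on day 6 after five days at 20 to 40 mg/kg, and fluid is more plentiful early: 38 × (0.707 + 0.841) ≈ 59 of 76 catheters are still in at day 14 at the design medians. This is a reason to keep week 2, not a reason to stop there.
- **Dose may not matter.** A reader might infer that 15 mg/kg/day is inactive because it lies below the 20 to 60 mg/kg range. The documents do not support that. The range is described as suitable for further testing, not as a threshold, and the evidence is mixed: the two phase I studies saw a plateau or no dose trend at 20 mg/kg and above, while the epirubicin study, which included 15 mg/kg, reported a positive correlation with dose.
- **Later fluid is collected.** Section 3.0 justifies ten weeks partly by examining fluid at several on-treatment points, and stored samples could be assayed afterwards. That is possible, but no later H3/H4 assay is planned.
- **The dose-escalation figure is not shown.** It may settle the order of visit and call. Either order falls within the bounds above, and a further condition could only delay step-up beyond the 10-day minimum.
- **Blood at week 6 is not assured.** Section 3.4.4 says "serum and plasma banking, and optional CTC (if patient agrees) assessment will be collected prior to treatment and at weeks 2, 6 and 10", but the Study Parameters table lists blood and fluid as optional, and the cited acetylation results came from tumour, peripheral blood or mononuclear cells rather than serum. This stands as a limit on the fix.

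**Conclusion.** The point holds as a modest one. Within week 2, the only planned on-treatment H3/H4 sample is taken at 15 mg/kg/day or no more than 3 days into 30 mg/kg/day. The full-dose period has no planned measurement: 56 to 60 of 70 days for a step-up on days 11 to 15, or 45 to 47 if a late visit delays it to days 24 to 26. This rests on section 2.1 governing the assay schedule, since sections 1.0 and 2.3.2 name no time points. The documents do not define how long at full dose counts as established.

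Two stronger inferences should be avoided. It cannot be said that every week-2 sample is at half dose, because the call is undated in sections 3.4 and 5.0 and may come first. Nor does the trial's main inference suffer: alpha, power and the primary endpoint are untouched. What is weakened is a secondary objective and the reading of a null result. Because the remedy is cheap, it should be made.

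**What to change.** In the fourth aim of section 2.1, add week 6 to the H3/H4 measurement, using the week-6 blood and pleural fluid already scheduled, from patients who provide them. Keep week 2. With every sample, record the current dose and the days since step-up, and analyse each by the dose actually being taken. Leave the order and timing of the step-up call as they are: requiring the visit to come first could delay full dose for some patients.

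The cost is one more assay round, with no new visit and, provided the banked week-6 blood suits the assay, no new draw. Blood is bounded by 76 patients and will be fewer because some will decline or have stopped treatment. Week-6 fluid comes only from patients whose catheter is still in, about 36 to 40 of 76 at the design medians under exponential times. State in advance that the week-6 between-arm comparison rests on the blood-based measure and that the fluid result is read as selected by outcome.

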4.0 Patient Eligibility

4.0 Eligibility Criteria

4.1 Inclusion Criteria

- Patients with symptomatic pleural effusion requiring placement of an IPC.
- Pathologic documentation of breast cancer.
- Performance status 0 to 3 (ECOG scale).

- 4.1.4 Signed informed consent prior to the indwelling pleural catheter placement.
- 4.1.5 Subject must be female or male age 18 years or over.
- 4.1.6 At least one prior line of chemotherapy in the metastatic setting
- 4.1.7 Positive effusion cytology

4.2 Exclusion Criteria

- 4.2.1 Palliative radiation to the chest. (Palliative radiotherapy will be allowed to extra thoracic sites.)
- 4.2.2 No other prior malignancy is allowed except for adequately treated basal cell or squamous cell skin cancer, in situ cervical cancer, or other cancer from which the patient has been disease-free for at least two years.
- 4.2.3 Laboratory results sustained at: Neutrophils less than $1.5 \times 10^9/L$; Serum bilirubin $>1.5 \times$ the upper limit of reference range (ULRR); Serum creatinine $>1.5 \times$ ULRR or creatinine clearance $< 30 \text{ mL/minute}$ (calculated by Cockcroft-Gault formula).
- 4.2.4 Ionized calcium or magnesium out of normal range despite supplementation; Alanine aminotransferase (ALT) or aspartate aminotransferase (AST) $> 2.5 \times$ ULRR or alkaline phosphatase (ALP) $>2 \times$ ULRR, or $> 4 \times$ ULRR if judged by the investigator to be related to liver metastases.
- 4.2.5 Serious underlying medical condition that would impair the ability of the patient to receive protocol treatment, specifically cardiac diseases, uncontrolled hypertension or renal diseases.
- 4.2.6 Diagnosis of an infection requiring IV antibiotics 14 days prior to registration.
- 4.2.7 Any psychological, familial, sociological or geographical condition potentially hampering compliance with the study protocol and follow-up schedule.
- 4.2.8 Women who are currently pregnant or breast feeding.
- 4.2.9 Known hypersensitivity to VPA, valproate sodium, disodium valproate, or any ingredient in the respective formulation.
- 4.2.10 Known urea cycle disorders based on history.
- 4.2.11 Known HIV infection based on history.
- 4.2.12 Active or recent pancreatitis (within last 6 months).
- 4.2.13 Any of the following interventions on the affected hemithorax: prior IPC, prior chest tube placement, history of chemical or mechanical pleurodesis, history of thoracotomy within 4 weeks and incompletely healed surgical incision before randomization.
- 4.2.14 Evidence of empyema or history of empyema of the affected hemithorax
- 4.2.15 Non-correctable bleeding diathesis
- 4.2.16 Clinical evidence of skin infection at the potential site of IPC placement.
- 4.2.17 Patients currently taking valproic acid.
- 4.2.18 History of hepatitis or liver disease
- 4.2.19 The following drugs will not be administered concurrently with VPA.
 - Carbapenem antibiotics
 - Clonazepam
 - Topiramate
 - Felbamate
 - Lorazepam

- Barbiturates
- CarBAMazepine
- ChlorproMAZINE
- Ethosuximide
- GuanFACINE
- LamoTRIgine
- Methylfolate
- OXcarbazepine
- Paliperidone
- Phenytoin
- Primidone
- Protease Inhibitors
- Rifampin
- Risperidone
- Rufinamide
- Salicylates
- Temozolomide
- Tricyclic Antidepressants
- Vorinostat
- Zidovudine

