1.2.2 Safety Profile for VPA

Frequency of adverse effects by organ system:

>10%:

Central nervous system: Headache (>31%), somnolence (>30%), dizziness (12% to 25%), insomnia (>1% to 15%), nervousness (>1% to 11%), pain (1% to 11%)

Dermatologic: Alopecia (>1% to 24%)

Gastrointestinal: Nausea (15% to 48%), vomiting (7% to 27%), diarrhea (7% to 23%), abdominal pain (7% to 23%), dyspepsia (7% to 23%), anorexia (>1% to 12%)

Hematologic: Thrombocytopenia (1% to 24%; dose related)

Neuromuscular & skeletal: Tremor (>57%), weakness (6% to 27%)

Ocular: Diplopia (>1% to 16%), amblyopia/blurred vision (>12%)

Miscellaneous: Infection (>20%), flu-like syndrome (12%)

1% to 10%:

Cardiovascular: Peripheral edema (>1% to 8%), chest pain (>1% to <5%), edema (>1% to <5%), facial edema (>1% to <5%), hypertension (>1% to <5%), hypotension (>1% to <5%), palpitation (>1% to <5%), postural hypotension (>1% to <5%), tachycardia (>1% to <5%), vasodilation (>1% to <5%), arrhythmia

Central nervous system: Ataxia (>1% to 8%), amnesia (>1% to 7%), emotional lability (>1% to 6%), fever (>1% to 6%), abnormal thinking (>6%), depression (>1% to 5%), abnormal dreams (>1% to <5%), agitation (>1% to <5%), anxiety (>1% to <5%), catatonia (>1% to <5%), chills (>1% to <5%), confusion (>1% to <5%), coordination abnormal (>1% to <5%), hallucination (>1% to <5%), malaise (>1% to <5%), personality disorder (>1% to <5%), speech disorder (>1% to <5%), tardive dyskinesia (>1% to <5%), vertigo (>1% to <5%), euphoria (1%), hypoesthesia (1%)

Dermatologic: Rash (>1% to 6%), bruising (>1% to 5%), discoid lupus erythematosus (>1% to <5%), dry skin (>1% to <5%), furunculosis (>1% to <5%), petechia (>1% to <5%), pruritus (>1% to <5%), seborrhea (>1% to <5%)

Endocrine & metabolic: Amenorrhea (>1% to <5%), dysmenorrhea (>1% to <5%), metrorrhagia (>1% to <5%), hypoproteinemia

Gastrointestinal: Weight gain (4% to 9%), weight loss (6%), appetite increased

(·6%), constipation (>1% to 5%), xerostomia (>1% to 5%), eructation (>1% to <5%), fecal incontinence (>1% to <5%), flatulence (>1% to <5%), gastroenteritis (>1% to <5%), glossitis (>1% to <5%), hematemesis (>1% to <5%), pancreatitis (>1% to <5%), periodontal abscess (>1% to <5%), stomatitis (>1% to <5%), taste perversion (>1% to <5%), dysphagia, gum hemorrhage, mouth ulceration

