Genitourinary: Cystitis (>1% to 5%), dysuria (>1% to 5%), urinary frequency (>1% to <5%), urinary incontinence (>1% to <5%), vaginal hemorrhage (>1% to 5%), vaginitis (>1% to <5%)

Hepatic: ALT increased (>1% to <5%), AST increased (>1% to <5%)

Local: Injection site pain (3%), injection site reaction (2%), injection site inflammation (1%)

Neuromuscular & skeletal: Back pain (·8%), abnormal gait (>1% to <5%), arthralgia (>1% to <5%), arthrosis (>1% to <5%), dysarthria (>1% to <5%), hypertonia (>1% to <5%), hypokinesia (>1% to <5%), leg cramps (>1% to <5%), myalgia (>1% to <5%), myasthenia (>1% to <5%), neck pain (>1% to <5%), neck rigidity (>1% to <5%), paresthesia (>1% to <5%), reflex increased (>1% to <5%), twitching (>1% to <5%)

Ocular: Nystagmus (1% to 8%), dry eyes (>1% to 5%), eye pain (>1% to 5%), abnormal vision (>1% to <5%), conjunctivitis (>1% to <5%)

Otic: Tinnitus (1% to 7%), ear pain (>1% to 5%), deafness (>1% to <5%), otitis media (>1% to <5%)

Respiratory: Pharyngitis (2% to 8%), bronchitis (5%), rhinitis (>1% to 5%), dyspnea (1% to 5%), cough (>1% to <5%), epistaxis (>1% to <5%), pneumonia (>1% to <5%), sinusitis (>1% to <5%)

Miscellaneous: Diaphoresis (1%), hiccups

<1%, postmarketing, and/or case reports (limited to important and/or life-threatening):

Aggression, agranulocytosis, allergic reaction, anaphylaxis, anemia, aplastic anemia, asterixis, behavioral deterioration, bilirubin increased, bleeding time altered, bone marrow suppression, bone pain, bradycardia, breast enlargement, cutaneous vasculitis, carnitine decreased, cerebral atrophy (reversible), coma (rare), dementia, encephalopathy (rare), enuresis, eosinophilia, erythema multiforme, Fanconi-like syndrome (rare, in children), galactorrhea, hematoma formation, hemorrhage, hepatic failure, hepatotoxicity, hostility, hyperactivity, hyperammonemia, hyperammonemic encephalopathy (in patients with UCD), hyperglycinemia, hypersensitivity reactions (severe, with multiorgan dysfunction), hypofibrinogenemia,

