Aggression, agranulocytosis, allergic reaction, anaphylaxis, anemia, aplastic anemia, asterixis, behavioral deterioration, bilirubin increased, bleeding time altered, bone marrow suppression, bone pain, bradycardia, breast enlargement, cutaneous vasculitis, carnitine decreased, cerebral atrophy (reversible), coma (rare), dementia, encephalopathy (rare), enuresis, eosinophilia, erythema multiforme, Fanconi-like syndrome (rare, in children), galactorrhea, hematoma formation, hemorrhage, hepatic failure, hepatotoxicity, hostility, hyperactivity, hyperammonemia, hyperammonemic encephalopathy (in patients with UCD), hyperglycinemia, hypersensitivity reactions (severe, with multiorgan dysfunction), hypofibrinogenemia, hyponatremia, hypothermia, inappropriate ADH secretion, intermittent porphyria, LDH increased, leukopenia, lupus, lymphocytosis, macrocytosis, menstrual irregularities, pancytopenia, parkinsonism, parotid gland swelling, photosensitivity, platelet aggregation inhibited, polycystic ovary disease (rare), psychosis, seeing "spots before the eyes," Stevens-Johnson syndrome, suicidal behavior/ideation, thyroid function tests abnormal, toxic epidermal necrolysis (rare), urinary tract infection

BOX WARNINGS:

Hepatotoxicity

Potentially fatal hepatic failure can occur.

Usually occurs during the initial 6 months of therapy. Children <2 years of age are at considerably increased risk of developing fatal hepatotoxicity, especially those receiving multiple anticonvulsants and those with congenital metabolic disorders, severe seizure disorders accompanied by mental retardation, or organic brain disease. Above this age group, the risk of fatal hepatotoxicity decreases considerably in progressively older patient groups.

Serious fatal hepatotoxicity may be preceded by symptoms such as malaise, weakness, lethargy, facial edema, anorexia, and vomiting.

Monitor patients closely for development of any such changes.

Perform liver function tests prior to and at frequent intervals during therapy, especially during the first 6 months.

Fetal/Neonatal Morbidity and Mortality

Can produce teratogenic effects (e.g., neural tube defects such as spinal bifida).

Use in women of childbearing potential requires that potential benefits of therapy be weighed against the risk of fetal injury.

Pancreatitis

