5.3 Guidance on the management adverse events

Excluded reporting and recording of adverse events:

1. Alopecia
2. Differential component of CBC except WBC, ANC, platelet count and hemoglobin

Baseline reporting of adverse events prior to protocol treatment will not be recorded or reported. All other baseline adverse events will be reviewed and if worsen will be captured in Figures 2-9.

The eligibility criteria provide an extensive list of concomitant medication as exclusions. Non-Oncologic concomitant medications will not be reported.

5.3.1 Guidance on dose reduction for specified alterations in amylase, lipase, or liver enzymes.

Figure 1. CNS Adverse Event Management
Study drug dosing is for 10 total weeks. During treatment visits will correspond to the week the patient is actively administering drug.

[figure not shown]

Figure 3. Elevated Amylase and Lipase at any dose

Study drug dosing is for 10 total weeks. During treatment visits will correspond to the week the patient is actively administering drug.

[figure not shown]
[figure not shown]

Figure 4. Management of elevated AST or ALT

Study drug dosing is for 10 total weeks. During treatment visits will correspond to the week the patient is actively administer

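### Section 4.2 sets entry limits for neutrophils and six chemistry values but no minimum platelet count, although the protocol lists thrombocytopenia as a dose-related effect of valproate

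*Combined protocol and SAP*

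**What the plan says.** Section 4.2.3 excludes on "Laboratory results sustained at: Neutrophils less than" 1.5 × 10⁹/L, on bilirubin, and on creatinine or its clearance. Section 4.2.4 adds ionized calcium, magnesium, ALT or AST, and alkaline phosphatase. The criterion closest to platelets is 4.2.15, "Non-correctable bleeding diathesis", which carries no number. The inclusion criteria in 4.1 contain no laboratory value, and 4.3 deals only with contraception.

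Platelets are measured. Section 3.3.3 requires a CBC before treatment, within 7 days of enrollment. Section 3.4.4 lists "Blood samples for CBC with differential, platelet count, and PT/PTT/INR" before treatment and at weeks 2, 6 and 10. Section 5.3 keeps platelets reportable, because its exclusion from adverse-event recording covers only the "Differential component of CBC except WBC, ANC, platelet count and hemoglobin".

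On the drug itself, the >10% group of the adverse-effect list in 1.2.2, repeated in 5.1.4, has a single hematologic entry: "Thrombocytopenia (1% to 24%; dose related"). The <1% and postmarketing group of the same list includes "platelet aggregation inhibited". Section 5.1.4 also calls bone marrow suppression the primary toxicity at 30 mg/kg/day with other chemotherapy, and 5.1.6 admits patients on current chemotherapy.

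**The concern.** The protocol fixes numeric entry limits for seven analytes, so it did not leave laboratory fitness to judgment alone. The one blood count that its own list puts among the more frequent valproate effects is not among them. Every patient has had at least one line of chemotherapy for metastatic disease (4.1.6), and some will be receiving more during the ten weeks on study drug.

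At stake is who may start the drug. Someone whose platelets are already low could be randomized, start valproate, and later have the dose doubled, without any criterion asking whether the count was adequate for that exposure.

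**Working it through.** There is no stated figure to reproduce and no sample-size formula applies. The check is a reading of all entry criteria against the safety sections.

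1. **Analytes with an entry limit.** 4.2.3: neutrophils, bilirubin, creatinine (or its clearance) = 3. 4.2.4: ionized calcium, magnesium, ALT/AST (counted once), alkaline phosphatase = 4. Total 3 + 4 = 7, that is, one blood count and six chemistry values. Platelets are not among them, and no platelet threshold appears elsewhere in the text. The eligibility section shows no redaction. The figures missing from the text used here belong to 5.2 and 5.3, on dosing and adverse-event management, not to entry.

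2. **What the valproate list says.** Thrombocytopenia is in the >10% group. The effects closest to the neutrophil limit are in the <1% and postmarketing group: agranulocytosis (in the run beginning "Aggression, agranulocytosis, allergic reaction, anaphylaxis, anemia, aplastic anemia") and leukopenia. On this list alone, the count with an entry limit is the rarer problem and the count without one is the more frequent.

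3. **What the summarized cancer studies say (1.2.1).** The evidence here points the other way.
   - Oral phase I study, 20 to 40 mg/kg: one grade 1 lymphopenia was the laboratory change reported.
   - Intravenous phase I study: hematologic toxicity rare and mild.
   - Epirubicin study: febrile neutropenia.
   - Neoadjuvant study with hydralazine: grade 3/4 neutropenia in 35% and anemia in 15%.
   - Refractory-tumor study with hydralazine: hematologic toxicity lowered dose intensity in nine patients (60%), cell line not given.
   - Chemoradiation study with hydralazine: increased myelotoxicity, cell line not given.

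   None names thrombocytopenia. The neutrophil limit is therefore well founded, and the case for a platelet limit rests on the general list.

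4. **Provisions that act before the first dose.**
   - Pretreatment CBC and PT/PTT/INR (3.3.3): measured, but no eligibility decision is attached to the platelet result.
   - 4.2.15: excludes only a diathesis that cannot be corrected.
   - 4.2.19: bars concurrent salicylates, which removes one added bleeding risk.
   - Standard-of-care catheter decision (3.3): concerns one procedure. Study drug starts that same day if cytology is positive (3.4), and a count corrected for the procedure says nothing about ten weeks of valproate.
   - 4.2.5: serious underlying conditions, specified as cardiac disease, uncontrolled hypertension or renal disease.

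   None sets a platelet value.

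5. **Provisions that act only after dosing begins.** These are the counts at weeks 2, 6 and 10, the dose-reduction steps in 5.2, the discontinuation rule in 7.0, and the stopping rule in 6.0 for toxicity leading to dose reduction. Section 5.3 adds that "All other baseline adverse events will be reviewed and if worsen will be captured in Figures 2-9"; by their titles those charts manage events on treatment. They were not available for this check, and nothing is assumed about their content.

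6. **Exposure permitted.** A patient admitted with a low count starts at 15 mg/kg/day. If this is tolerated for 10 consecutive days the dose rises to 30 mg/kg/day, a ratio of 30/15 = 2. The rise is conditional, not automatic.

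**The case against.** The strongest reply is that choosing laboratory cut-offs is clinical judgment, and that the neutrophil-only limit follows the trial-level evidence, in which neutropenia and anemia are named and thrombocytopenia is not. Section 5.1.6 adds that valproate at this dose has been documented with FEC and is in routine use alongside chemotherapy for metastatic breast cancer. Exclusion 4.2.15 can fairly be read to cover clinically important thrombocytopenia that cannot be corrected. The dose rise depends on tolerance, which the note to the study-parameters table places at the 2-week visit, when a platelet count is also drawn.

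Much of this stands. It limits the weight of the evidence and shows that severe cases may be caught in practice. It does not close the gap at entry. A low but correctable count passes 4.2.15, and the week-2 count comes after dosing has begun. The escalation instruction can also be given by telephone, so the text does not guarantee that the count is read first.

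A reader might also count the four CBC items still recorded as adverse events, note that only neutrophils has an entry limit, and take that as a measure of risk. It is not one. Hemoglobin has no limit either, and white cell count overlaps with neutrophils.

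**Conclusion.** The omission is real and minor. As written, a patient with a low platelet count and no non-correctable bleeding diathesis is eligible to start valproate. The conclusion rests on the eligibility text being complete as shown, and on the general adverse-effect list being relevant to these patients.

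Three stronger readings are tempting, and the documents do not support them.

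- **A number of patients harmed.** Applying 1% and 24% to the planned valproate arm of 76/2 = 38 gives 38 × 0.01 = 0.38 and 38 × 0.24 = 9.12. These would be on-treatment cases at general valproate rates. They do not say how many candidates would enter with a low count, or how many of those would come to harm. The documents give neither figure.
- **A monitoring gap.** Platelets are counted on study and remain reportable, and the management charts were not seen. The gap is at entry only.
- **An effect on the statistical design.** Nothing here touches power, alpha, accrual or the toxicity stopping rule.

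**What to change.** Add a minimum platelet count to 4.2.3, beside the neutrophil limit, judged on the CBC already drawn within 7 days of enrollment. The documents give no basis for a particular cut-off, so the sponsor's clinicians should set it. No other change is needed.

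The cost is one eligibility line in an amendment, with no new test or visit. The downside is that a few candidates become ineligible or need a repeat count; how many cannot be computed from the documents.
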